12. PROGRAMMING SPECIFICATIONS

All outputs will be produced using SAS version 9.4 or a later version.

The margins should be at least 1.50 inches for the binding edge and 1.0 inches for all other edges.

In the top left portion of each table/listing, the sponsor's name, *protocol number*, *type of analysis* (*Draft or Final*) will be presented. In the top right portion of each table/listing, page X of Y will be presented. On the next line, a *table/listing number* followed by the *title* of the table/listing and

population information will be displayed. Horizontal lines will appear after the column heading of the table/listing. *Footnotes* will be put under the main body of text at the bottom of the page. The source listing number will be displayed for all tables. The *SAS program name, Source Data, Extract date and Cut-off date* will appear bottom left in a string of each table/listing. The *date and time of creation* of table/listing will appear bottom left under to the SAS program name line.

Times New Roman, proportional 8-point bold font will be used for all tables and listings. Usually, a landscape layout is suggested for both tables and listings, but it is not mandatory. Any date information in the listing will use the date9. format, for example, 07MAY2002.

Shells for unique tables and listings are provided in a separate Mock-Up TFLs document.

13. LIST OF TABLES, LISTINGS, AND FIGURES

Shells for unique tables, listings and figures are provided in a separate Mock-Up tables, figures, and listings (TFLs) document.

15. APPENDIX I. SCHEDULE OF ASSESSMENTS**TABLE 14-1 SCHEDULE OF ASSESSMENTS**

Study Procedure	Screening Visit	Treatment Period						EoS / ET	F/U
		Cycle 1							
Cycle (C) #	-	Cycle 1						Cycle 2-35	
Cycle # and Day		C1D1	C1D2	C1D4	C1D8	C1D11	C1D15	D1	
Window period (days)	-28 to -1	-1 [*]	±1	±3	±3	±3	±3	±3	±7
Informed consent ^a	X								
Demographics	X								
Eligibility screening	X	X							
Medical history ^b	X	X							
Physical examination ^c	X	X			X*			X	X
Height, weight ^d	X ^d	X						X	X
Vital signs ^e	X	X						X	X
Ophthalmology examination ^f	X							Q6wk for the first 6 months, then Q9wk thereafter ^f	X
ECOG ^g	X							X	X
12-lead ECG ^h	X	X		X ^g					X
Pregnancy testing ⁱ	X								X
Tumor biopsy ⁱ	X								
Hematology and serum chemistry ^k	X	X			X		X	Every week for Cycles 2 and 3, then D1 of Cycles 4+	X
Coagulation and urinalysis ^l	X							D1 of each 21-day cycle ^l	X
Drug administration ^m		X						D1 of each 21-day cycle	
Pharmacokinetic								See footnote n	

sample ⁿ								See footnote o	X	X ⁿ
Immunogenicity (ADA) ^p		X								
Radiology evaluations (CT or MRI) ^p	X							Q6wk for the first 3 months, then Q9wk thereafter	X	
Concomitant medications		↔							↔	
Adverse events			↔							

Abbreviations: ADA = anti-drug antibody; D = Day; C = Cycle; CT = computed tomography; ECG = electrocardiogram; ECOG = Eastern Cooperative Oncology Group; EoS = End of Study; ET = Early Termination; F/U = follow-up; MRI = magnetic resonance imaging; Q6wk = every 6 weeks; Q9wk = every 9 weeks

EoS Visit is the safety follow-up visit, conducted 28 ± 7 days after the last OBI-999 dose. ET Visit lab assessments will be conducted for patients discontinuing study treatment, if last available tests are before 2 weeks.

*The - 1 day window (1 day prior) for C1D1 is for safety laboratory assessments. Blood can be drawn 1 day prior to initiation of study drug infusion on C1D1. Safety laboratory results should be available and reviewed by the Investigator prior to the OBI-999 administration.

Footnotes:

- a. Informed consent to be obtained before any other study procedures are performed.
- b. Medical history, including previous cancer therapies, cancer history, and past and ongoing concomitant illnesses which are relevant to the disease under study.
- c. A complete physical examination is required at screening and end of study/early termination. Directed physical examinations may be limited to problem focused review of symptoms and major organ systems. This should include an assessment for signs and symptoms of peripheral neuropathy as this is a known adverse event associated with MMAE-based ADCs and may be expected to occur with OBI-999.
- d. Height to be obtained at screening only.
- e. Vital signs include temperature, blood pressure and pulse. Temperature measurement will be obtained as clinically indicated.
- f. Performed by ophthalmologist as follows:
 - a. Part A - At screening, every 2 cycles for the first 6 months (C2, C4, C6, C8), then every 3 cycles thereafter (C11, C14 and so on), and the end of study/early termination visit.
 - b. Part B – At screening and at the discretion of the Investigator during the course of the study.
- g. ECOG performance status: at screening, D1 of each cycle, and end of study/early termination

- h. 12-lead ECG with assessment of QTcF: at screening, Cycle 1 Day 1, Cycle 1 Day 3 (48± 2 hours after the end of the Cycle 1 Day 1 OBI-999 infusion) and EoS/ET. The ECG testing on C1D4 could be tested 24 hours before but no later than C1D4.
- i. Pregnancy testing should be performed in females of childbearing potential only. A serum pregnancy test is required during screening. A urine or serum pregnancy test is acceptable end of study or early termination
- j. Tumor biopsy samples are mandatory at screening visit. Fresh (preferred) tissue or archival tissue is acceptable. A minimum of 5 slides are required for the central laboratory Globo H assay for determination of eligibility in Part B. Up to 10 unstained additional slides should be provided, depending on availability, for the protocol defined exploratory studies.
- k. Hematology and Serum chemistry (Laboratory Assessments: Protocol Table 12-1). Blood draw is prior to OBI-999 infusion. For C2D1 and each cycle after, laboratory assessments may be drawn 72 hours in advance of infusion.
Hematology: hematocrit, hemoglobin, erythrocyte count, white blood count, absolute counts of leukocytes, neutrophils, lymphocytes, monocytes, eosinophils, basophils, and platelet count.
Serum chemistry: sodium, potassium, chloride, bicarbonate, blood urea nitrogen, creatinine, glucose, calcium, phosphorus, magnesium, total protein, albumin, alanine aminotransferase, aspartate aminotransferase, alkaline phosphatase, creatine kinase, lactate dehydrogenase, total bilirubin, and uric acid. Creatinine clearance will be calculated by Cockcroft Gault equation at screen visit, week 1 and EoS/ET.
- l. Coagulation, and Urinalysis (Laboratory Assessments: Protocol Table 12-1). Blood draw and urine collection is prior to OBI-999 infusion. Only urinalysis will be collected at Day 1 of Cycles 2-35.
Coagulation: prothrombin time, activated partial thromboplastin time, and international normalized ratio.
Urinalysis: specific gravity, pH, protein, glucose, ketones, bilirubin, urobilinogen, blood, nitrite, leukocyte esterase as assessed by dipstick. A microscopic urinalysis (only if needed) evaluating white blood cells, red blood cells, epithelial cells, bacteria, cast and crystals
- m. OBI-999 is given on Day 1 of each 21-day cycle until DLT, disease progression, unacceptable toxicity, or withdrawal of consent, whichever occurs earlier.
- n. Pharmacokinetic: (for analysis of serum concentration of OBI-999 total antibody, ADC and free MMAE). Detailed sampling schedule in Table 14.2 (Part A) and Table 14.3 (Part B).
- o. Immunogenicity studies (ADA) - ADA samples will be collected. Detailed sampling schedule in Table 14.2 (Part A) and Table 14.3 (Part B). For patients with persistent antibodies at end of study, an additional ADA sample will be collected at 4 months after the end of study visit.
- p. Radiology (CT or MRI scan) evaluations of tumor response: Performed during screening and during the study every 6 weeks for the first 3 months, and then every 9 weeks until discontinuation of study treatment, disease progression, death, or initiation of further systemic cancer therapy, including radiation therapy, whichever occurs earlier. CT or MRI scan will be performed within 1 week prior to the start of the next cycle. Unscheduled scan can be performed anytime, if needed to confirm disease progression. Radiology assessment for early

termination/end of study, should ONLY be performed if ≥ 9 weeks have passed from the previous scheduled CT/MRI scan. Same assessment method and same technique should be used on each patient while on study.

TABLE 14-2 PART A - PHARMACOKINETIC AND ADA SAMPLING SCHEDULE

Cycle	Cycle 1 and Cycle 2						Cycle 3 and Cycle 4		Cycle 5-8, 12 and every 4 cycles thereafter	EoS / ET
Cycle Day	D1	D2	D4	D8	D11	D15	D1	D8	D1	±7 days
Pharmacokinetic Samples										
Before infusion	X ^a						X ^b		X ^b	
30 minutes after end of infusion (90 min) ^c	X	X ^d	X	X ^d	X	X				
2 hours after end of infusion (180 min) ^{c,e}	X									
4 hours after end of infusion (300 min) ^{c,e}	X									
8 hours after end of infusion (540 min) ^{c,e}	X									
Immunogenicity Studies (ADA)^f	X						X		X	X

Abbreviations: ADA = anti-drug antibody; C = Cycle; D = Day; EoS = End of Study; ET = Early Termination; min = minute

OBI-999 infusion should be administered on Day 1 of every 21-day cycle throughout the study treatment period.

The infusion duration of Cycle 1 and Cycle 2 are 60 ± 10 minutes and can be reduced to 30 ± 10 minutes from Cycle 3, if there were no infusion related adverse events on prior infusions and at the discretion of the Investigator.

- Cycle 1 Day 1 (C1D1) pre-infusion serum samples can be drawn within 1 day prior-to the infusion.
- Pre-infusion serum samples can be collected at any time prior to the infusion on the day of the infusion.
- Post-infusion samples on D1 can be collected in a window of ± 15 minutes.
- Samples on Days 2, 4, 8, 11, and 15 can be collected in a window of ± 2 hours based on the end of infusion on Day 1.

- e. If there is change of the infusion rate or interruption of infusion, the PK sampling on Day 1 is to be collected from the exact time of completion of infusion to obtain the post-infusion samples after the end of infusion. Exact time of sample collection and the reason for interruption should be documented in the eCRF.
- f. ADA samples will be collected along with pre-infusion PK samples. No post-infusion ADA samples will be collected. For subjects with persistent antibodies at end of study, an additional ADA sample will be collected at 4 months after the end of study visit.

TABLE 14-1 PART B - PHARMACOKINETIC AND ADA SAMPLING SCHEDULE

Cycle	Cycle 1 and Cycle 2					Cycle 3, Cycle 4, Cycle 8, and Every 4 Cycles Thereafter	EoS / ET
Cycle Day	D1	D2	D4	D8	D15	D1	±7 days
Pharmacokinetic Samples							
Before infusion	X ^a					X ^b	
30 minutes after end of infusion (90 min) ^c	X	X ^{d,g}	X ^{d,g}	X ^d	X ^d	X	X
6 hours after end of infusion (420 min) ^{c,e}	X						
Immunogenicity Studies (ADA)^f	X					X	X

Abbreviations: ADA = anti-drug antibody; C = Cycle; D = Day; EoS = End of Study; ET = Early Termination; min = minute

OBI-999 infusion should be administered on Day 1 of every 21-day cycle throughout the study treatment period.

The infusion duration of Cycle 1 and Cycle 2 are 60 ± 10 minutes, and can be reduced to 30 ± 10 minutes from Cycle 3, if there were no infusion related adverse events on prior infusions and at the discretion of the Investigator.

- a. Cycle 1 Day 1 (C1D1) pre-infusion serum samples can be drawn within 1 day prior-to the infusion.
- b. Pre-infusion serum samples can be collected at any time prior to the infusion on the day of the infusion.
- c. Post-infusion samples on D1 can be collected in a window of ± 15 minutes.
- d. Samples on Days 2, 4, 8, and 15 can be collected in a window of ± 2 hours based on the end of infusion on Day 1.
- e. If there is change of the infusion rate or interruption of infusion, the PK sampling on Day 1 are to be collected from the exact time of completion of infusion to obtain the post-infusion samples after the end of infusion. Exact time of sample collection and the reason for interruption should be documented in the eCRF.
- f. ADA samples will be collected along with pre-infusion PK samples. No post-infusion ADA samples will be collected. For subjects with persistent antibodies at end of study, an additional ADA sample will be collected at 4 months after the end of study visit.
- g. This intensive PK sampling will be collected from first 5 patients in each cohort.

16. APPENDIX II IMPUTATION RULES FOR MISSING DATES

Algorithm for Treatment-emergent Adverse Events

AE Start Date	AE Stop Date	Action
Known	Known	If start date < study drug start date, then not TEAE If start date \geq study drug start date, then TEAE
	Partial	If start date < study drug start date, then not TEAE If start date \geq study drug start date, then TEAE
	Missing or Unknown	If start date < study drug start date, then not TEAE If start date \geq study drug start date, then TEAE
Partial, but the known date components show that it cannot be on or after study drug start date	Known	Not TEAE
	Partial	Not TEAE
	Missing or Unknown	Not TEAE
Partial, could be on or after study drug start date	Known	If stop date < study drug start date, then not TEAE If stop date \geq study drug start date, then TEAE
	Partial	Impute stop date as latest possible date (i.e., last day of month if day is unknown or 31-Dec if day and month are unknown), then: If stop date < study drug start date, then not TEAE If stop date \geq study drug start date, then TEAE
	Missing or Unknown	Assumed TEAE
Missing or Unknown	Known	If stop date < study drug start date, then not TEAE If stop date \geq study drug start date, then TEAE
	Partial	Impute stop date as latest possible date (i.e., last day of month if day is unknown or 31st December if day and month are unknown), then: If stop date < study drug start date, then not TEAE If stop date \geq study drug start date, then TEAE
	Missing or Unknown	Assumed TEAE

Algorithm for Concomitant Medications

CM Start Date	CM Stop Date	Action
Known	Known	If stop date < study drug start date, assign as PRIOR If stop date \geq study drug start date, assign as CONCOMITANT
	Partial	Impute stop date as latest possible date (i.e., last day of month if day unknown or 31-Dec if day and month are unknown), then: If stop date < study drug start date, assign as PRIOR If stop date \geq study drug start date, assign as CONCOMITANT
	Missing or Unknown	Assign as CONCOMITANT
Partial	Known	If stop date < study drug start date, assign as PRIOR If stop date \geq study drug start date, assign as CONCOMITANT
	Partial	Impute stop date as latest possible date (i.e., last day of month if day unknown or 31-Dec if day and month are unknown), then: If stop date < study drug start date, assign as PRIOR If stop date \geq study drug start date, assign as CONCOMITANT
	Missing or Unknown	Assign as CONCOMITANT
Missing or Unknown	Known	If stop date < study drug start date, assign as PRIOR If stop date \geq study drug start date, assign as CONCOMITANT
	Partial	Impute stop date as latest possible date (i.e., last day of month if day unknown or 31-Dec if day and month are unknown), then: If stop date < study drug start date, assign as PRIOR If stop date \geq study drug start date, assign as CONCOMITANT
	Missing or Unknown	Assign as CONCOMITANT

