## **12.5 Adverse Events**

### **12.5.1 Adverse Events**

An AE is any symptom, physical sign, syndrome, or disease that either emerges during the study period or worsens during the study, regardless of the suspected cause of the event. All medical and psychiatric conditions (except those related to the indication under study) present at screening will be documented in the medical history eCRF. Changes in these conditions and new symptoms, physical signs, syndromes, or diseases should be noted on the AE eCRF during the rest of the study. Clinically significant laboratory abnormalities should also be recorded as AEs. Surgical procedures that were planned before the patient enrolled in the study are not considered AEs if the conditions were known before study inclusion; the medical condition should be reported in the patient's medical history.

Patients will be instructed to report AEs at each study visit. All AEs are to be followed until resolution or until a stable clinical endpoint is reached.

Each AE is to be documented on the eCRF with reference to date of onset, duration, incidence, severity, relationship to study drug, action taken with study drug, treatment of event, and outcome. Furthermore, each AE is to be classified as being serious or non-serious. Changes in AEs and resolution dates are to be documented on the eCRF.

For the purpose of this study, treatment emergent AEs will be collected starting from the time the patient receives the first dose of study drug (from Cycle 1 Day 1) until 28 days after the last dose of study drug. Follow-up of the AE, even after the date of therapy discontinuation, is required if the AE persists until the event resolves or stabilizes at a level acceptable to the Investigator.

Specific guidelines for classifying AEs by intensity (Grade) and relationship to study drug are given in Table 12-2 and [Table 12-3](#). The severity of AEs will be graded according to the NCI CTCAE version 5.0 (Grades 1 to 5).

When changes in the intensity of an AE occur more frequently than once a day, the maximum intensity for the event should be noted.

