#### **14.5 Safety Analysis**

Adverse events will be coded according to Medical Dictionary for Regulatory Activities (MedDRA) version 21.0 or higher and assessed for severity using NCI CTCAE version 5.0. Adverse events will be summarized by system organ class and preferred term and presented in decreasing order of incidence. Dose-limiting toxicities will also be summarized by dose and cohort. The incidence of TEAEs (events with onset dates on or after the start of the study drug) will be included in incidence tables. Events with missing onset dates will be included as treatment-emergent. If a patient experiences more than 1 occurrence of the same AE, the occurrence with the greatest severity and the closest association with the study drug will be used in the summary tables. Serious adverse events and AEs causing discontinuation will be tabulated. All AEs will be listed by patient, along with information regarding onset, duration, relationship and severity to study drug, action taken with study drug, treatment of event, and outcome.

Vital signs, ECG data, ophthalmology, hematology, serum chemistry, coagulation, and urinalysis parameters from baseline and during study will be examined. Treatment-emergent changes in key laboratory parameters will be identified. Clinical laboratory data will be summarized for each time point that specimens are collected. Changes from baseline, for select clinical laboratory analytes may also be explored as specified in the SAP.

Summary tables will be provided for concomitant medications initiated prior to study enrollment or during the study period.

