10.3 HANDLING OF MISSING DATA

Partial or missing start and end dates of AEs and concomitant medications will be imputed conservatively based on the rule described in Appendix II: Imputation rules for missing dates. The imputed dates will be used to allocate the AEs and concomitant medications to a study period, and to determine whether an AE is/is not treatment emergent. Listings of the AEs and concomitant medications will present the actual partial dates; imputed dates will not be shown in the listings.

For ORR endpoint, patients with missing data (for any reason) will be included as non-responders in the statistical analysis for each related follow-up analysis. For analyses performed in the safety population, patients who discontinue due to toxicity or clinical progression prior to post-baseline tumor assessments will be considered as non-responders and retained in the denominator.

For CBR endpoint, patients with missing data (for any reason) will be included as non-responders in the statistical analysis for each related follow-up analysis.

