10.7.1 PRIMARY ENDPOINTS

PART A (DOSE-ESCALATION)

A. AEs/ SAEs and laboratory abnormalities as graded by NCI CTCAE version 5.0*.

Treatment emergent adverse events (TEAEs) are defined as AEs with onset dates on or after the start of study drug until 28 days after the last dose of study drug or if it is present prior to receipt of the study treatment but worsens in severity or increases in frequency on or after the first dose. AEs having both onset and end dates missing will be considered as TEAEs.

TEAEs will be summarized by study part, cohort (by dose level in Part A and by cancer type in Part B), SOC, PT, severity grade, and relationship to treatment. SAEs, deaths, and AEs leading to early treatment discontinuation (collected on Adverse Events eCRF page) will be summarized. The summaries will be sorted by decreasing order of overall incidence of SOCs and decreasing order of overall incidence of PTs within SOCs.

Events reported as “Unrelated” or “Unlikely related” to study drug will be considered as unrelated to the study drug. Events reported as “Possibly related”, “Probably related”, “Definitely related” to study drug or without relationship information will be considered as related to the respective treatment.

Overview summaries of the number and percentages of patients and number of events within the following categories will be provided by study part and by cohort (by dose level in Part A and by cancer type in Part B):

- Any TEAE
- Any TEAE grade ≥ 3
- Any TEAE related to OBI-999
- Any Serious TEAE
- Any Non-Serious TEAE
- Any Serious TEAE related to OBI-999
- Any TEAE leading to death
- Any TEAE leading to discontinuation of OBI-999 (defined as AE with an action taken equals to “Drug Withdrawn”)
- Any Serious TEAE leading to discontinuation of OBI-999 (defined as AE with an action taken equals to “Drug Withdrawn”)
- Any TEAE leading to study discontinuation (defined as AE flagged as Grade 4 infusion reactions and OBI-999 related toxicity, or intercurrent illness in the “End of Study” eCRF

page)

- Any Serious TEAE leading to study discontinuation (defined as AE flagged as Grade 4 infusion reactions and OBI-999 related toxicity, or intercurrent illness in the “End of Study” eCRF page)

Tables by SOC and PT will be displayed for following AEs. Only those AEs marked with * will be analyzed in the aCSR as per sponsor decision.

- TEAEs*
- TEAEs grade ≥ 3 *
- TEAEs related to OBI-999*
- Serious TEAEs*
- Non-Serious TEAEs

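### SAP Appendix II classes pre-dose adverse events that worsen on drug as not treatment-emergent, against SAP 10.7.1; the effect is probably small and may be nil

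*SAP*

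**What the plan says.** SAP 10.7.1 defines a TEAE in two limbs. The first is an onset window: "onset dates on or after the start of study drug until 28 days after the last dose of study drug". The second covers an event already there at first dose: it also counts "if it is present prior to receipt of the study treatment but worsens in severity or increases in frequency" on or after that dose.

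SAP 10.3 says "Partial or missing start and end dates of AEs and concomitant medications will be imputed conservatively" by the rules of Appendix II, and that the imputed dates serve, among other things, "to determine whether an AE is/is not treatment emergent". The appendix is headed "APPENDIX II IMPUTATION RULES FOR MISSING DATES".

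Its TEAE algorithm nevertheless begins with rows for a known start date, including one where the stop date is also known. Each of these rows says "If start date < study drug start date, then not TEAE" and makes any later onset a TEAE. Where a partial start date can only be pre-dose, the result is not TEAE for all three types of stop date. No row mentions worsening, frequency, last dose or 28 days.

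The Protocol is not uniform either. Section 14.5 describes "TEAEs (events with onset dates on or after the start of the study drug") and stops there. Section 12.5.1 includes worsening in its definition of an AE and has treatment-emergent events collected "from Cycle 1 Day 1) until 28 days after the last dose of study drug".

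**The concern.** The SAP gives two answers for the same event. A programmer working from 10.7.1 counts a pre-dose event that worsens on drug, and a programmer working from the appendix table drops it. For an onset more than 28 days after last dose the error runs the other way, because the known-start rows keep what 10.7.1 excludes. SAP Section 11 does not mention the difference. Protocol Section 14 lets the SAP override the Protocol, but that does not rank one part of the SAP above another.

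The affected outputs are kept for the abbreviated report. AEs are a primary endpoint in Part A and a secondary endpoint in Part B, and the main TEAE tables and listings are starred. The listing of pre-treatment AEs is not starred, and Section 11 drops the medical history outputs. A worsened event classed as not TEAE would therefore have no other planned AE or medical history output in which to appear. Dropping such an event is also hard to square with the conservative handling that 10.3 promises.

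**Working it through.** There is no planned figure to reproduce. The check compares the two rules, first row by row and then on test cases.

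**Row by row.** Appendix II has 4 types of start date × 3 types of stop date = 12 TEAE rows.

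| Start date | Rows | Pre-dose event that worsens on drug | Onset after last dose + 28 days |
|---|---|---|---|
| Known | 3 | not TEAE: conflict | TEAE: conflict |
| Partial, must be pre-dose | 3 | not TEAE: conflict | cannot arise |
| Partial, could be on or after first dose | 3 | TEAE: agrees | TEAE: conflict if the known components show a late onset |
| Missing | 3 | TEAE: agrees | TEAE: cannot be tested |

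The last two groups lose no worsened event. Four of their rows decide on the stop date and two assume TEAE. An event that worsens after first dose has a stop date on or after first dose, or an unknown one, and a partial stop date is moved to its latest possible value. So 3 + 3 = 6 of the 12 rows can drop a worsened event. If the appendix is held to partial and missing start dates, 3 rows can.

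**Test cases with a known start date.** Assume first dose on Day 1 and three 21-day cycles. Last dose is then Day 1 + 2 × 21 = Day 43, and the 10.7.1 window ends on Day 43 + 28 = Day 71.

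| Event | SAP 10.7.1 | Appendix II |
|---|---|---|
| Pre-dose, no worsening | not TEAE | not TEAE |
| Pre-dose, worsens on drug | TEAE | not TEAE |
| Onset Day 1 | TEAE | TEAE |
| Onset Day 71 | TEAE | TEAE |
| Onset Day 72 | not TEAE | TEAE |
| Onset Day 78 | not TEAE | TEAE |

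Day 78 is the latest end-of-study visit in this example: 28 ± 7 days after last dose gives at most 35 days, and 43 + 35 = 78.

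**Can such records exist?** Stated collection under Protocol 12.5.1, and SAE reporting under 12.5.3, run from Cycle 1 Day 1 to 28 days after last dose. Pre-dose onsets fall outside that period, and so do late ones. Collection and the TEAE window both end at day 28, so the late gap is 28 − 28 = 0 days unless a site records beyond the window, for example at a visit up to 35 − 28 = 7 days late. Still, SAP 10.7.1 plans separate listings of pre-treatment and post-treatment AEs, so its authors foresaw both kinds of record.

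**The case against.** The strongest reply is that the case hardly arises. Protocol 12.5.1 puts conditions present at screening on the medical history form and sends changes in them to the AE form, and Protocol 8.6.1 likewise has a worsening concomitant illness documented as an AE. The AE record is then the change itself. It would naturally carry an on-study onset, and both rules would call it a TEAE. Most of this stands. What is missing is a stated rule for the onset date. If a worsening always received a new on-study date, the worsening limb of 10.7.1 would have little to do.

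A second reply is that the appendix governs incomplete dates only, so a known start date never reaches it. The title and 10.3 support this, and 10.7.1 is the natural rule for complete dates. But the table contains a row with both dates known, and no sentence tells the programmer to ignore it. The three partial-but-pre-dose rows conflict with 10.7.1 even on the narrow reading.

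A third reply is that the late-onset side is nearly empty, because collection stops where the TEAE window stops. That stands, and it is why this side is secondary.

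A reader might infer that worsening of baseline neuropathy will vanish from the report, since Exclusion Criterion 3 bars only Grade 2 or greater and Protocol 8.3.2.1 foresees worsening. The documents do not support that. Low-grade neuropathy at screening follows the medical-history route above, and neither provision says how an AE is dated.

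**Conclusion.** Wrong as written, and minor. Appendix II is inconsistent with the TEAE definition in SAP 10.7.1. The conflict is certain in the three partial-but-pre-dose rows, and it extends to the three known-start rows if they are applied. The known-start rows also lack the limit at last dose plus 28 days.

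The number of misclassified records is not given and may be zero. An effect requires that a worsening is held under its pre-dose onset date, or that a site records an onset beyond the collection window.

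A reader might turn this into percentage points: one patient is 1/3 = 33.3 points among the three enrolled at the lowest dose level, or 1/22 = 4.5 points in Part A if all 22 were dosed. Neither is an estimate. The first uses an extreme denominator, and a single record changes a table row only if that patient has no other event counted in the row.

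Dose-limiting toxicities are analysed as collected on the eCRF and the recommended Phase 2 dose is already set, so neither is affected.

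**What to change.** 1. State in SAP 10.3 and at the head of Appendix II that 10.7.1 decides TEAE status when the AE start date is known, and that the appendix applies only to partial or missing start dates. Delete the three known-start rows or mark them *apply 10.7.1*.
2. In the three partial-but-pre-dose rows, replace the result by *Not TEAE unless the event worsened in severity or increased in frequency on or after first dose (10.7.1)*. Protocol 12.5.1 already requires changes in AEs on the eCRF.
3. Optionally, in the three rows for partial dates that could be on or after first dose, add *not TEAE if the known components show onset later than last dose + 28 days*. The missing-start rows can stay as they are.

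No note in SAP Section 11 is needed, because Protocol Section 14 leaves the detailed definitions to the SAP. The cost is a few lines of text and a small derivation change. No new data are needed if AE changes were recorded as required.
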